## SCHEMA

\*Pre-Study Requirements are specific to each patient

\* If scheduling or safety prevents all lesions from being irradiated within one day, participants will complete Cycle #2 of Nelfinavir then undergo a minimum of 7 days “clear out”. Following this break participants will repeat Cycle #1 of Nelfinavir then receive radiation to the remaining lesions followed by a repeat Cycle #2 of Nelfinavir. This process may not exceed three “rounds” of treatment (NFV1, SBRT, NFV2) and may include repeat imaging and/or blood work.

## 1. PROTOCOL SYNOPSIS

TITLE	Single-Arm Phase II Study of Stereotactic Body Radiation Therapy Concurrent with Nelfinavir for Oligometastases
STUDY PHASE	Phase II
INDICATION	Patients presenting with oligometastatic disease, where metastases are limited in number and location.
PRIMARY OBJECTIVES	
 
To determine the 6-month freedom from local progression rate of the radiosensitizer Nelfinavir used concurrently with 15 Gy of stereotactic body radiation therapy (SBRT) delivered in 1 fraction (per lesion) in patients with oligometastatic disease
 

SECONDARY OBJECTIVES	
 
To assess the toxicity of the radiosensitizer Nelfinavir used concurrently with 15 Gy of stereotactic body radiation therapy (SBRT) delivered in 1 fraction(per lesion) in patients with oligometastatic disease
 
To determine local control at 6 months after SBRT delivered to a dose of 15 Gy in 1 fraction (per lesion) combined with Nelfinavir in patients with oligometastatic disease
 
To assess long-term clinical outcomes of this patient population after completion of SBRT in combination with Nelfinavir
 
To assess quality of life following completion of SBRT in combination with Nelfinavir
 
To determine the correlation between phospho-Akt levels and lesion response rate
 

HYPOTHESES	Concurrent SBRT and Nelfinavir will achieve greater than 70% freedom from local progression 6 months.
STUDY DESIGN	Patients with metastatic lesions of the lung, liver, or bone will be candidates for treatment. Within three weeks of the initial treatment planning, a 15 Gy dose (per lesion) of SBRT will be administered. Prior to SBRT, patients will initiate Nelfinavir oral therapy twice daily for 7 days. Once SBRT is completed, the patient will repeat the same Nelfinavir therapy for an additional 7 days for a total of 14 days of treatment.
SAMPLE SIZE BY TREATMENT GROUP	42 patients total
SUMMARY OF SUBJECT ELIGIBILITY CRITERIA	
 
Metastasis at one or more of the following sites: bone, liver, and/or lung. No more than 5 lesions will be treated.
 
Tumor(s) to be treated is(are) <math>\leq 5.0</math> cm or <math>\leq 250</math> cm^3.
 
Age <math>\geq 18</math> years.
 
ECOG performance status <math>\leq 2</math>.
 
Histologic confirmation of malignancy (primary or metastatic tumor).
 

INVESTIGATIONAL PRODUCTS DOSAGE AND ADMINISTRATION	Commercially available Nelfinavir (1250 mg) will be administered orally twice daily for 14 days.
CONTROL GROUP	N/A
PROCEDURES	1. Physical exam 2. Blood draw 4. CT or MRI of Involved Site 5. PET-CT (all are optional) 6. SBRT + oral Nelfinavir administration

## 2. ABBREVIATIONS AND DEFINITIONS OF TERMS

Abbreviation	Definition
ADL	Activities of daily living
AE	Adverse event
BID	Twice daily
BSA	Body surface area
CBC	Complete blood count
CI	Confidence interval
C MAX	Maximum concentration of drug
CNS	Central nervous system
CRF	Case report/Record form
CR	Complete response
CTCAE	Common Terminology Criteria for Adverse Events
DLT	Dose Limiting Toxicity
DSMB	Data Safety Monitoring Board
ECG	Electrocardiogram
GI	Gastrointestinal
Hgb	Hemoglobin
HIV	Human Immunodeficiency Virus
HPF	High-power field
HTN	Hypertensions
IRB	Institutional Review Board
IV	Intravenous
LLN	Lower limit of normal
MTD	Maximum tolerated dose
OS	Overall survival
PLT	Platelet
PD	Progressive diseased
PFS	Progression free survival
PR	Partial response
QD	Once daily
RECIST	Response evaluation criteria in solid tumors
RR	Response rate
SAE	Serious adverse event

Abbreviation	Definition
SBRT	Stereotactic body radiation therapy
SD	Stable disease
TTP	Time to progression
ULN	Upper limit of normal
UNK	Unknown
WBC	White blood cell
WHO	World Health Organization

### **3. OBJECTIVES**

#### **3.1 Primary Objective**

To determine the 6-month freedom from local progression rate of the radiosensitizer Nelfinavir used concurrently with 15 Gy of stereotactic body radiation therapy (SBRT) delivered in 1 fraction (per lesion) in patients with oligometastatic disease.

#### **3.2 Secondary Objectives**

To assess the toxicity of the radiosensitizer Nelfinavir used concurrently with 15 Gy of stereotactic body radiation therapy (SBRT) delivered in 1 fraction (per lesion) in patients with oligometastatic disease.

To determine local control at 6 months after SBRT delivered to a dose of 15 Gy in 1 fraction (per lesion) combined with Nelfinavir patients with oligometastatic disease.

To assess long-term clinical outcomes of this patient population after completion of SBRT in combination with Nelfinavir.

To assess quality of life following completion of SBRT in combination with Nelfinavir.

To determine the correlation between Phospho-Akt levels and lesion response rate.

### **4. BACKGROUND**

#### **4.1 Oligometastatic Disease**

Cancer is the second leading cause of death in the United States, chiefly from an inability to control metastatic disease. Systemic therapy alone is not curative for patients with most metastatic solid tumors.(1) The metastatic capacity of cancers behaves along a spectrum of disease progression, such that some tumors have spread widely before clinical detectability and others never metastasize. Contained within this spectrum, is an oligometastatic state where metastases are limited in number and location. The presence of an oligometastatic state was originally proposed by Hellman who suggested that these oligometastatic patients would benefit from effective local therapy in addition to systemic therapy.(1) In agreement with this hypothesis, surgery and chemotherapy for isolated pulmonary metastases can result in long term disease-free periods. (2) Additionally, some 25% of patients following

resection and chemotherapy for colorectal cancer and isolated liver metastases can similarly have long-term disease free survival.(3)(4)(5)

The treatment of metastases depends on multiple factors including 1) the location of the primary tumor, 2) the presence or absence of other metastatic foci, 3) the size, number and location of metastases, 4) the effectiveness of various forms of therapy (such as surgery, radiation and chemotherapy), and 5) patient's functional status. Extracranial metastatic tumors most often referred for local therapy in the form of resection include colon cancer, sarcomas, germ cell tumors, and melanoma metastatic to the lung. For the more common primary tumors such as those of breast and lung, metastases are rarely referred for resection as chemotherapy (or hormonal manipulation) is generally considered to be the primary mode of treatment.

#### **4.2 Stereotactic Body Radiation Therapy (SBRT)**

Conventional moderate dose radiation for metastatic disease is given primarily for palliation. Recent advancements in radiation delivery now make it possible to image and treat precisely within any anatomical region of the body.(6, 7) As a result, the capacity to deliver tumor killing radiation doses in a single or few (1-5) outpatient radiation treatments is now possible.(8-12) In addition, by minimizing the irradiation of surrounding healthy tissue, it should also be possible to decrease the rate of complications. Intracranial stereotactic body radiation therapy (SBRT) has been shown to be a highly effective treatment for brain metastases.(13) This suggests that selective small extracranial tumors (either primary or metastatic tumors) may be effectively controlled by similar focal high-dose SBRT. There is an increasing experience with extracranial SBRT as effective local therapy for metastatic lesions. Local control in excess of 75% has been reported for metastatic tumors of the spine, lung and liver, which is significantly higher than standard conventional moderate dose radiation.(9, 11, 12, 14)(15) Toxicity has been minimal in multiple U.S., European and Japanese trials of extracranial stereotactic radiotherapy to the lung, liver, spine, pelvis and abdomen despite the use of very high biological equivalent doses for patients with both organ confined and metastatic cancer.

#### **4.3 Tumor Hypoxia**

Another factor potentially limiting the efficacy of SBRT or hypofractionated regimens is intratumoral hypoxia. Tumor hypoxia is a well substantiated poor prognostic factor for multiple tumor types and increases tumor cell radioresistance. A several week course of fractionated radiation therapy can partially mitigate tumor hypoxia because death of well oxygenated tumor cells allows for reoxygenation of more hypoxic clonogens in a tumor. The efficacy of SBRT or hypofractionated regimens are susceptible to tumor hypoxia because treatment is delivered in an abbreviated course not allowing for tumor reoxygenation. A normoxic and hypoxic tumor selective radiosensitizer in combination with SBRT would hypothetically overcome barriers to intratumoral hypoxia.

#### **4.4 Nelfinavir**

A compound ideally situated to meet the requirements as a normoxic and hypoxic tumor selective radiosensitizer is the HIV protease inhibitor Nelfinavir. The first report of an antitumoral activity of an HIV protease inhibitor (HPI) was published in 1999 as a case

report. The normoxic radiosensitizing effect of Nelfinavir has been well characterized *in vitro* and *in vivo* and has been linked to the inhibition of phospho-Akt which is overexpressed in many different types of solid tumors, but not normal tissues. Nelfinavir can radiosensitize hypoxic cells within a tumor by decreasing HIF-1 $\alpha$  expression and vascular endothelial growth factor (VEGF) release resulting in angiogenesis inhibition and improved tumor oxygenation. Nelfinavir also sensitizes endothelial cells to radiation-induced death. Finally, utilization of Nelfinavir (Viracept; F. Hoffmann-La Roche Ltd, Basel, Switzerland) as an anticancer agent would have the advantage that the drug has already been used for more than a decade in the clinic and its safety profile is well defined. Retrospective data from HIV positive patients taking routine doses of HPIs concurrently during conventional radiation therapy suggests no increased normal tissue toxicity. (37, 38)

#### 4.5 Rationale for Use in Pulmonary Metastasis

Pulmonary tissue represents a fertile area for metastatic seeding from epithelial malignancies. Aggressive management with surgical resection has resulted in good outcomes. For example, in the International Registry of Lung Metastases, over 5000 cases of lung metastasectomy are recorded.

Multiple series have shown local control for primary lung tumors of >90% using stereotactic body radiotherapy in medically inoperable patients.(16-19)(20) A related series compared outcomes of wedge resection versus SBRT in primary lung cancer and found improved local control with SBRT.(21) These studies report acceptable toxicity profiles with a low risk of grade III or greater toxicity. Consequently, two randomized trials are investigating the role of SBRT versus surgery in medically fit patients. This includes the Dutch ROSEL trial which randomizes operable stage T1N0 patients to surgery versus SBRT as well as the STARS trial which randomizes operable stage 1 (<4cm) patients to surgery versus SBRT.

Taken together, less invasive techniques such as SBRT are now being applied in place of metastasectomy in oligometastatic disease to target pulmonary metastasis. Multiple institutions have reported favorable outcomes using either single or multi-fraction SBRT for oligometastatic sites within the lung. Wulf et al. prescribed 26 Gy in single fraction and reported a 90% local control at 9 months.(22) Hof and colleagues report 63% progression free survival at 3 years using 12-30 Gy prescribed to the isocenter.(23) Le treated primary early stage and metastatic lung tumors with SBRT using doses of 15-30 Gy and report a local control of 91% for doses greater than 20 Gy and 54% for doses less than 20 Gy.(11)

Single dose fraction of 15 Gy with SBRT to the lung is used to allow for acceptable toxicity and to meet dose constraints when multiple pulmonary targets are treated. Single dose SBRT is limited by treatment toxicity at higher doses. Le and colleagues report a 12.5% rate of grade 2 to 3 pneumonitis and a 9.4% rate of possible treatment related death when single SBRT doses of greater than 25 Gy were given. However, toxicity was rare when doses of less than 25 Gy were given.(11) The potential for multiple targets in the oligometastatic setting results in difficulty in achieving pulmonary tissue constraints when

doses of >25 Gy are applied to each target. An attractive alternative is to dose reduce radiation while giving a radiation sensitizer.

A dose of 15 Gy will allow for safe targeting of multiple pulmonary metastases. Radiosensitizing effects of Nelfinavir may improve local control to mirror those results with higher dose radiation while providing acceptable toxicity. To date, there is no literature to suggest an increased rate of pneumonitis or other pulmonary toxicity with concurrent administration of Nelfinavir and radiation.

Reports of SBRT in pulmonary metastasis are heterogeneous. Most reports of metastatic lung tumors include medically inoperable patients with a primary lung malignancy. While some groups report equivalent outcomes, others reports decreased local control with metastatic versus primary lung cancer. For example, Le et al., report a 1 year freedom from local relapse of 92% for primary NSCLC compared with 44% for metastatic lesions with doses >20 Gy are given.(11) Additionally, series report a heterogeneous dose of radiation given, making direct comparisons by dose difficult. However, early reports of control do provide a basic framework from which to compare the efficacy of Nelfinavir with SBRT compared to those treated with higher doses of RT alone.

#### **4.6 Rationale for Use in Liver Metastasis**

The primary management of unresectable metastatic disease to the liver is systemic chemotherapy. Some uncontrolled trials have investigated liver-directed therapies such as transarterial embolization (TACE), radioembolization, stereotactic body radiation therapy (SBRT), chemoradiation (CRT), radiofrequency ablation, and cryotherapy in the palliative or, in rare cases, neoadjuvant setting(15, 24-27). Liver metastases are a common source of cancer morbidity and mortality and are often the only site of metastases. Major advancements in radiation treatment planning and delivery have resulted in resurgence in the use of radiation therapy (RT) as a treatment for liver tumors. With the development of 3-dimensional conformal radiation treatment (CRT), partial liver irradiation became possible. Stereotactic body radiation therapy (SBRT) is defined as highly focused, stereotactic localized, high-dose RT delivered in a hypofractionated course. In selected patients, very high local control rates have been observed, with minimal toxicity. Patients most likely to benefit from RT are those with liver confined disease, focal distribution of metastases, and metastases more than 1.5 cm from luminal gastrointestinal organs.

Chemotherapy and molecular-targeted agents rarely eradicate metastases permanently. For colorectal carcinoma liver metastases, selected resection series have yielded 5-year survival rates of approximately 50% showing that local therapy has the potential to cure “oligo” or isolated liver metastases (5, 9, 28-31). Patients are not suitable for resection because of medical or surgical reasons. The benefit of local therapy in non-colorectal liver metastases is less clearly defined, but long-term survival has been reported after the resection of liver metastases from sarcoma, breast cancer, and other tumor sites (32).

The dose-limiting toxicity from whole-liver RT is radiation-induced liver disease (classic RILD), initially called radiation hepatitis (33-35)and characterized pathologically by central vein occlusion as described by Reed and Cox.(36)With the advent of 3-dimensional

conformal radiation treatment (CRT) planning and delivery technology that allows for partial liver irradiation, and that higher tumor doses could be delivered safely as long as the mean dose to the liver was kept to less than safely tolerated whole-liver doses. At the University of Michigan, no cases of RILD after CRT for colorectal liver metastases were seen when the mean liver dose was <31 Gy in 1.5 Gy twice a day. This group also found the Lyman normal tissue complication probability model useful as a means of relating dose-volume histogram data to risk of liver toxicity (35). In recent years, the application of stereotactic body radiation therapy (SBRT) has allowed even more intensive tumor dose escalation in a hypofractionated schedule with increased conformality that limit the dose to the liver usually well below the threshold above which severe RILD is observed(15).

It is now recognized that some patients with “oligo,” or few sites of metastases, may have isolated sites of metastases that can be potentially cured with local therapy. The term “oligometastases” was coined to refer to this stage of distant metastases. Typically, the entire burden of disease can be recognized as a finite number of discreet lesions. Although there is no strict definition of oligometastases, it is commonly interpreted to be no more than 5 or 6 metastatic sites. Milano et al. (9) from the University of Rochester have also shown that the net tumor burden for patients with 5 or fewer sites of macrometastatic disease, treated on 2 prospective SBRT protocols, was an independent predictor of overall outcome. Whether SBRT, as an adjunct to systemic therapy, to selected macroscopic metastases can influence overall survival by keeping the burden of disease below such a “lethal threshold” is being investigated.

Goodman et al.(15) reported a phase I dose-escalation single-fraction trial for patients with liver metastases or intrahepatic cholangiocarcinoma. Doses were escalated in 4-Gy cohorts from 18 Gy up to 30 Gy in 1 fraction. Twenty-six patients with 40 lesions were treated. There was no dose-limiting toxicity. The median follow-up was 17 months, and this corresponded to a 12-month local control rate of 77%. The 2-year actuarial survival rate was 50.4%.

Based on data above, in this study we will evaluate whether a Nelfinavir plus a single fraction of SBRT can be combined with Nelfinavir to control liver metastases with up to 5 liver metastases. Patients will be closely monitored for grade 3 or above liver toxicity including RILD.

#### **4.7 Concurrent SBRT and Nelfinavir**

The use of radiation therapy to treat metastatic tumors is well established and promising data are emerging with the use of SBRT for metastatic disease. However, the use of a single large fraction concurrent with a radiosensitizer as is being proposed is not of proven benefit. This investigation aims to confirm the safety and efficacy for SBRT used concurrently with a radiosensitizer in the setting of oligometastatic disease. The dose selected has been chosen with the belief that it is safe and effective based on prior experience with SBRT of lung cancer, pancreatic cancer and brain radiosurgery. All patients will be treated with a single fraction, targeted to the lesion concurrently with the radiosensitizer Nelfinavir.

On the basis of this preclinical evidence, we propose a phase I-II study of Nelfinavir combined with SBRT in patients with oligometastatic disease. Because the standard dose of Nelfinavir for HIV patients is known to be safe and does inhibit the phosphorylation of Akt and decrease tumor hypoxia, we propose to study this in conjunction with a 15 Gy dose of SBRT. Experience with single-fraction pulmonary and pancreas SBRT provides a useful dose for this trial. With published data establishing the relative safety of large single-fraction SBRT to the lungs and pancreas, we have decided to proceed to determine the safety of 15 Gy SBRT concurrently with the radiosensitizer Nelfinavir. Once this is established, we propose to continue to enroll more patients to the study at this dose to determine the efficacy of this type of therapy.

In general metastatic disease carries an extremely high mortality rate. Current therapies provide only partial palliation of symptoms and mild to moderate prolongation of survival. Patients are rarely cured of this disease; consequently, better treatment is clearly needed. The proposed treatment represents a logical extension of the current state-of-the-art radiation therapy. It has the potential to translate into more effective palliation and longer patient survival. Another advantage to the patient is that several weeks of radiation therapy can be accomplished in a single day, which is not inconsequential for patients with a limited life expectancy.

The proposed study represents an informed estimate based on current knowledge of SBRT doses and those administered in currently approved image-guided protocols (brain, base of skull, cervico-thoracic spine, pancreas and liver). This study will refine the current understanding of single fraction radiation tolerance for normal tissues, thereby making it possible to treat future patients more safely and aggressively.

## **5. PARTICIPANT SELECTION AND ENROLLMENT PROCEDURES**

*All patients will be eligible to receive chemotherapy alone or conventional chemo-radiotherapy at the time of clinical or radiographic disease progression or at 4 weeks post-treatment.*

## 5.1 Inclusion Criteria

- 5.1.1 Patient's tumor(s) to be treated is(are)  $\leq 5.0$  cm or  $\leq 250$  cm^3
- 5.1.2 Patient must have metastasis at one or more of the following sites: bone, liver, lymph node and/or lung. No more than five lesions will be treated.
- 5.1.3 Histological confirmation of malignancy (primary or metastatic tumor).
- 5.1.4 Patient may have any prior therapy allowed aside from having had prior radiotherapy to the treatment site (see exclusion criteria 5.2.3).
- 5.1.5 Patient must be  $\geq 18$  years of age.
- 5.1.6 Patient must have a life expectancy  $\geq 9$  months.
- 5.1.7 Patient must have an ECOG performance status  $\leq 2$ .
- 5.1.8 Patient must have normal organ and marrow function as defined as:

Leukocytes	$\geq 2,000/\mu\text{L}$
Absolute Neutrophil Count	$\geq 1,000/\mu\text{L}$
Platelets	$\geq 50,000/\mu\text{L}$
- 5.1.9 Patient must have the ability to understand and the willingness to sign a written informed consent document.

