### 11.3 Disease Parameters

Measurable Disease: Measurable lesions are defined as those that can be accurately measured in at least one dimension (longest diameter to be recorded) as  $\geq 10$  mm with diagnostic techniques (CT, PET/CT (all are optional), or MRI). All tumor measurements must be recorded in millimeters (or decimal fractions of centimeters).

Non-Measurable Disease: All other lesions (or sites of disease), including small lesions (longest diameter  $< 10$  mm with diagnostic techniques), are considered non-measurable disease. Bone lesions, leptomeningeal disease, ascites, pleural/pericardial effusions, lymphangitis, inflammatory breast disease, abdominal masses (not followed by CT or MRI), and cystic lesions are all non-measurable.

Target Lesions: Target lesions in this study will be considered oligometastatic sites up to a maximum of 5 lesions per patient. They should be recorded and measured at baseline. Target lesions should be equal to or larger than 10 mm in the smallest cross-sectional diameter on CT or MRI and/or any lesion that shows increase metabolic uptake on PET/CT scans. A sum of the longest diameter (LD) for all target lesions will be calculated and reported as the baseline sum LD. The baseline sum LD will be used as reference by which to characterize the objective tumor response.

Non-Target Lesions: N/A

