#### **11.5 Response Criteria (via RECIST 1.1)**

##### **11.5.1 Evaluation of Target Lesions**

Complete Response (CR): Disappearance of all target lesions

Partial Response (PR): At least a 30% decrease in the sum of the longest diameter (LD) of target lesions, taking as reference the baseline sum LD

Progressive Disease (PD): At least a 20% increase in the sum of the LD of target lesions, taking as reference the smallest sum LD recorded since the treatment started or the appearance of one or more new lesions

Stable Disease (SD): Neither sufficient shrinkage to qualify for PR nor sufficient increase to qualify for PD, taking as reference the smallest sum LD since the treatment started

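### Eligibility limits the lesions treated but not the metastases present, and section 11 has no progression criterion for a baseline lesion that is not a target

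*Combined protocol and SAP*

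**What the plan says.** **Population.** The synopsis gives the indication as "Patients presenting with oligometastatic disease, where metastases are limited in number and location". The title and objectives also name oligometastatic disease. Section 4.6 notes that no strict definition exists and that "it is commonly interpreted to be no more than 5 or 6 metastatic sites". Its closing paragraph speaks of up to five liver metastases.

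**Eligibility.** Section 5.1.2 reads "Patient must have metastasis at one or more of the following sites: bone, liver, lymph node and/or lung" and adds "No more than five lesions will be treated". The synopsis carries the same limit on treated lesions, but its site list omits lymph node.

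**Treatment.** Section 6.2 provides for further rounds when not all lesions can be irradiated in one day, which suggests that all lesions are expected to be treated. No section says so outright.

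**Lesion categories.** Section 11.3 says "Target lesions in this study will be considered oligometastatic sites up to a maximum of 5 lesions per patient" and "Non-Target Lesions: N/A". Section 11.5.2 repeats that non-target evaluation does not apply.

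**Progression.** Section 11.5.1 gives two routes to progressive disease: "At least a 20% increase in the sum of the LD of target lesions", measured from the smallest recorded sum, "or the appearance of one or more new lesions". Under 11.5.3, best overall response rests on target lesions alone.

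**Endpoints.** Sections 11.5.5 and 15.1.2 word the PFS event as tumor or disease progression, or death; TTP in 11.5.5 also uses tumor progression. Section 15.6 treats each metastatic lesion as a target for lesion-level local control, and lists time to distant progression (TTDP), which is defined nowhere.

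**The concern.** The response section works only if every known lesion is a target. The eligibility criteria do not ensure that. A patient with more metastases than will be irradiated, or with disease outside the listed sites, meets every numbered criterion. The lesions left over then have no category in section 11.

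Two things are at stake. First, PFS, TTP, response and duration of response could be scored differently by different assessors, and under the literal section 11 criteria they would miss real progression. Second, without a stated limit or a record of lesion counts, a reader of the results could not tell how far the enrolled patients match the oligometastatic population in the title.

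**Working it through.** The plan states no figure on this point, so there is none to reproduce. The check sets the sections side by side and then illustrates the size.

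**1. Does any criterion limit metastases present?** The only lesion count in 5.1 and 5.2 is the five treated lesions. The site requirement is a minimum (one or more listed sites), and no exclusion concerns disease elsewhere. The indication is qualitative, and the five-or-six figure in 4.6 is background. Baseline CT or MRI covers involved sites and PET-CT is optional (6.1, 6.2, section 10), so total burden need not be established.

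**2. What happens to a baseline lesion that is not a target?**
- It does not enter the target sum, so the 20% rule cannot detect its growth.
- It was present at baseline, so it is not a new lesion.
- The non-target category is marked not applicable, so there is no third route.

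Its growth therefore meets neither route in 11.5.1.

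**3. Do other sections close the gap?** PFS and TTP refer to progression in general terms, but 11.5.1 holds the only operational definition. TTDP has none. Section 15.6 makes every metastatic lesion a target, but 11.3 allows five per patient. With 15 metastases, 15 − 5 = 10 cannot be targets under 11.3. If 15.6 prevailed instead, unirradiated lesions would enter the local-control proportion, which is meant to measure the effect of SBRT.

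**4. Illustration of the target-sum rule (assumed sizes).** Five treated 20 mm lesions stay unchanged: target sum 100 mm, change 0%, stable disease.

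| Untreated 20 mm lesions | Their growth | Sum over all lesions | Change |
|---|---|---|---|
| 5 | 50% | 200 to 250 mm | +25% |
| 5 | 100% | 200 to 300 mm | +50% |
| 10 | 50% | 300 to 400 mm | +33% |
| 10 | 100% | 300 to 500 mm | +67% |

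Every row exceeds 20% over all lesions, yet 11.5.1 records stable disease if only the treated lesions are targets.

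**5. Size for 6-month PFS (assumed inputs).** Let s be the share of entrants with at least one untreated metastasis, and g the share of those who by 6 months have progressed only there and so are counted as event-free. Overstatement = s × g:
- 0.10 × 0.30 = 0.03, or 3 points
- 0.20 × 0.50 = 0.10, or 10 points
- 0.30 × 0.60 = 0.18, or 18 points

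If untreated growth is instead taken as independent of the counted events, with an assumed counted PFS of 60%, PFS including that growth is 0.60 × (1 − s × g), where g is now the share with any untreated growth:
- s = 10%, g = 30%: 0.60 × 0.97 = 58.2%, a gap of 1.8 points
- s = 30%, g = 60%: 0.60 × 0.82 = 49.2%, a gap of 10.8 points
- s = 50%, g = 70%: 0.60 × 0.65 = 39.0%, a gap of 21 points

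**6. Primary endpoint.** Section 15.5 defines freedom from local progression (FFLP) by local progression and keeps patients with distant metastasis on study. Growth of an untreated lesion is outside that endpoint by design.

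**The case against.** The strongest reply is that the protocol plainly intends an oligometastatic population with all lesions treated. The indication limits number and location, 4.6 speaks of up to five liver metastases, 6.2 plans for all lesions to be irradiated, and life expectancy of at least 9 months with ECOG of at most 2 works against high-burden entry. On that reading there are no non-target lesions. The PFS and TTP wording would also let an assessor count visible progression anywhere, and 15.6 makes every metastasis a target.

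Part of this stands. A reader might infer that untreated growth counts nowhere. The documents do not support that, because PFS, TTP and the undefined TTDP could each capture it as worded. What is true is that no defined criterion counts it and that sections 11 and 15 disagree. A reader might also infer that the trial could not speak for oligometastatic disease at all. That goes too far, since the indication does restrict entry, though without a number, and baseline lesion counts could be reported.

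The intent does not close the gap. An indication without a number cannot be applied uniformly, and the treatment text never requires that all disease be treated. Even if it did, 11.3 classes bone lesions and lesions under 10 mm as non-measurable, and makes target status depend on size or on uptake on an optional PET-CT. Some treated lesions may therefore still not be targets.

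**Conclusion.** The point holds for the secondary endpoints and for the description of the population. No numbered criterion limits the metastases present, and section 11 gives no progression criterion for a baseline lesion that is not a target, in conflict with 11.5.5, 15.1.2 and 15.6. PFS, TTP and response can miss progression.

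The size is unknown, because the documents do not give the share of entrants with untreated lesions. The 3 to 18 points are products of assumed inputs. The bias is zero if no entrant has such lesions, or if assessors count their growth under the general PFS wording.

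A further tempting inference is that higher disease burden biases the primary result through more censoring before the 6-month scan. The documents give no figure for this, and the required life expectancy of at least 9 months exceeds the 6-month horizon. FFLP is local and not directly biased. The change should be made, but the primary analysis does not depend on it.

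**What to change.** 1. In 11.3 and 11.5.2, replace the not-applicable entry. Record every known baseline lesion that is not a target (untreated, non-measurable or under 10 mm) as non-target, and add its unequivocal progression to the definition of progressive disease for PFS, TTP and overall response.
2. In 15.6, restrict lesion-level local control to irradiated lesions, and define TTDP.
3. Reconcile 5.1.2 and the synopsis with the indication, 4.6 and 6.2: state the maximum total number of known metastases at entry and whether untreated disease is allowed. The number and the rule are for the sponsor to set. Align the two site lists on lymph node, and report baseline lesion counts.

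An entry limit alone is not enough, because treated bone or small lesions may still fall outside target status. The cost is an amendment to these sections, slightly more imaging review and possibly a slightly lower reported PFS. An entry limit may exclude a few patients.
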